## 6.6 SAFETY ANALYSES

The safety listings will include the evaluation of the following data:

- Adverse events (AEs)
- Laboratory results
- Vital signs: pulse rate, respiration rate, temperature, systolic and diastolic blood pressure, and weight
- Electrocardiograms (ECGs)
- Physical exams
- ECOG Status

The SAF will be used for displaying safety outputs unless otherwise specified. Data will be provided in subject listings.

### 6.6.1 ADVERSE EVENTS

### 6.6.1.1 ADVERSE EVENT DEFINITIONS

Adverse events will be coded into standardized terminology according to the Medical Dictionary for Regulatory Activities (MedDRA) dictionary v23.0 or higher. Severity of AE will be graded according to National Cancer Institute Common Terminology Criteria for Adverse Events Version 5.0 (NCI CTCAE, v5.0).

- Treatment-Emergent Adverse Events (TEAEs) are designated as events that occur after the start of study drug(s), and were not observed prior to start of treatment; Or if the event was observed prior to the start of study drug but worsened after the start of study drug in the rollover study.
- Treatment Related TEAEs will include those TEAEs which are considered related to study drugs as designated by the investigator and/or Sponsor.
- Serious adverse events (SAEs) will include all events classified as serious on the eCRF. The electronic database used to enter data at the site will be deemed as the source of record for adverse event information. The safety and pharmacovigilance database will be reconciled against the EDC.
- Immune-related adverse events (irAEs) are unique side effects typically seen after dosing with checkpoint inhibitors and are derived based on eCRF irAE flag. Some of the most common irAEs include: pneumonitis, colitis, hepatitis, endocrinopathy , adrenal insufficiency, hypothyroidism and hyperthyroidism, , nephritis, dermatitis, and neuropathy Summary of Adverse Events

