10.8.2 Observation and Recording of AEs

AEs that occur on the parent study and are ongoing at the time of entry into the rollover study will be recorded as medical history. Any such AE that worsens on the rollover study should be recorded as a new AE at the worsened severity.

Study personnel will assess AEs at every visit. The date of onset and resolution (if applicable) of the AE will be documented in the source documents and on the appropriate eCRF page. The Investigator will monitor all AEs to the final study visit or to a satisfactory resolution if the AE is ongoing.

All AEs will be recorded from the time of signed informed consent until the End-of-study visit (28 days \pm 7 days after the last dose of study drug[s]) and are to be recorded on the appropriate AE pages in the eCRF and in source documents. AEs for the End-of-study visit may be collected by a telephone contact if the subject is not able to attend an on-site End-of-study visit. Where possible, a diagnosis rather than a list of symptoms should be recorded. If a diagnosis has not been made, then each symptom should be listed individually.

All study drug related AEs/SAEs (see [Section 10.8.4](#) for definition) will be followed to resolution (the subject's health has returned to his/her baseline status or all variables have returned to normal), or until new therapy initiated. Where appropriate, medical tests and examinations will be performed to document resolution of the event(s).

SAEs will be reported as outlined in [Section 10.9](#) and recorded in the AE eCRF.

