10.9.5 E-mail: [name]

Additional follow-up information, if required, or available, should be recorded on a follow-up SAE Report Form and faxed to IQVIA Drug Safety within one business day of discovery by site.

All SAEs, whether related or unrelated to study drug, will be recorded from the time of signed informed consent until resolution or new therapy initiated or for 28 days post final dose if no new therapy is initiated. Any SAEs considered to have at least a possible relationship to the study drug and discovered by the Investigator at any time period after the subject's study treatment has ended should be reported according to the timeframe described above.

Study drug-related SAEs will be followed until resolution, stabilization or subject receives new therapy.

At a minimum, the site number, Investigator's name, subject number, event name, the date of onset, a short description of the event and the Investigator's preliminary assessment of causality must be provided at the time of the initial SAE report.

The onset date of the SAE is defined as the onset date of signs and symptoms or a change in baseline when the SAE met seriousness criteria.

The resolution date of the SAE is defined as the date in which the criteria of seriousness is no longer applicable (e.g., discharge from hospitalization).

All SAEs that are ongoing events at the time of death should be considered not resolved at time of death.

The Investigator is encouraged to discuss with the Medical Monitor any SAEs for which the issue of reportability is unclear or in question.

The Investigator must review, sign, and date the SAE Report Form to confirm the accuracy of the information recorded on the SAE Report Form along with the corresponding source documentation.

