## Statistical Analysis Plan Version draft

## Protocol JTX-2011-R01

A general overview summary table will also be provided include frequencies by category of AE (as listed above) and will also include TEAE by severity grade and relationship to study drugs.

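### The SAP sets no end to the treatment-emergent window, so after about 28 days off drug a serious event can enter the TEAE counts only if it is judged related

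*SAP*

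**What the plan says.** **Definition.** SAP 6.6.1.1 has two limbs. A TEAE is one of the "events that occur after the start of study drug(s), and were not observed prior to start of treatment", or an event seen earlier that "worsened after the start of study drug in the rollover study". Both limbs fix a start and neither fixes an end. Treatment-related TEAEs are a subset of TEAEs, so they have no end either. SAEs are all events marked serious on the eCRF.

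**Collection.** Three windows apply:
- All AEs (Protocol 10.8.2): "All AEs will be recorded from the time of signed informed consent until the End-of-study visit", which is 28 ± 7 days after the last dose.
- All SAEs whatever the cause (Protocol 10.9.5, the SAE recording rules following 10.9.4): until resolution or new therapy, "or for 28 days post final dose if no new therapy is initiated".
- SAEs thought at least possibly related (same place): still to be reported when "discovered by the Investigator at any time period after the subject's study treatment has ended".

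**Route to the data.** Protocol 10.8.2 says SAEs are reported under 10.9 "and recorded in the AE eCRF". The SAP takes the site's electronic database as the source of record and reconciles the safety database against it.

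**Use.** SAP 3.1 puts TEAEs and serious TEAEs in the primary endpoint. The overview table in SAP 6.6.1.2 gives frequencies by AE category and "will also include TEAE by severity grade and relationship to study drugs".

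**The concern.** Once collection closes for events regardless of cause, the causality judgement decides whether a serious event is captured at all. The same judgement is then what the overview table reports. A related SAE months after treatment satisfies the TEAE definition and adds to the serious and related counts. An unrelated SAE on the same date has no route into the database.

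Long-term safety is the primary objective and there is no control arm, so readers will lean on the relationship split to judge what the drug does. That split would partly reflect how long and how actively sites keep in touch with former subjects. The related category is also mixed internally: its serious events have an open window, while its non-serious events stop at the End-of-study visit.

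**Working it through.** The documents give no event rates, sample size or power, so there is no planned figure to reproduce. The check has two parts.

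**1. Which events are captured, by time since last dose**

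| Event | To about day 28 | Later | Meets TEAE definition if later |
|---|---|---|---|
| Related SAE | collected | still reportable | yes |
| Unrelated SAE | collected | not collected | yes, but never recorded |
| Non-serious AE, any cause | collected to the visit (day 21 to 35) | not collected | yes, but never recorded |

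The only post-dose cut in the SAP is the 30-day split of deaths in the disposition summary (6.4.1). It is not applied to TEAEs.

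**2. How large the effect could be (illustrations; all rates and durations are assumed)**

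*Illustration A: equal, constant rates of related and unrelated SAEs.* Let D = 365 days on rollover drug, A = days after last dose in which a site might learn of events, and p = the fraction of late related SAEs reported.

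Related time captured = D + 28 + p(A − 28). Unrelated time captured = D + 28 = 393 days. The true related share is 50%.

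- A = 90, p = 0.25: 365 + 28 + 0.25 × 62 = 408.5. Ratio 408.5/393 = 1.04; share 408.5/801.5 = 51%.
- A = 180, p = 0.5: 365 + 28 + 0.5 × 152 = 469. Ratio 469/393 = 1.19; share 469/862 = 54%.
- A = 180, p = 1: 365 + 28 + 152 = 545. Ratio 545/393 = 1.39; share 545/938 = 58%.

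*Illustration B: true related share 25%.* Assume on-drug rates per month of u = 0.03 (unrelated) and r = 0.01 (related), and an off-drug rate m times the on-drug rate for both. T is months on drug, F is months after last dose in which late related SAEs are reported, and W = 28/(365.25/12) = 0.92 months.

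Unrelated = u(T + mW). Related, common window = r(T + mW). Related, open window = r(T + mF).

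- Low (T = 24, F = 6, m = 0.25): unrelated 0.03 × 24.23 = 0.727; related 0.01 × 25.5 = 0.255; share 0.255/0.982 = 26.0%. Related count × 1.05.
- Middle (T = 12, F = 12, m = 0.5): unrelated 0.03 × 12.46 = 0.374; related 0.01 × 18 = 0.180; share 0.180/0.554 = 32.5%. Related count × 1.44, total serious count × 1.11.
- High (T = 6, F = 24, m = 1): unrelated 0.03 × 6.92 = 0.208; related 0.01 × 30 = 0.300; share 0.300/0.508 = 59.1%. Related count × 4.34, total serious count × 1.83.

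With F = W (nothing reported late), or with one common cut-off, the share returns to 25.0% in every scenario.

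**The case against.** **Consequence is limited. This stands.** The study has no control arm and no hypothesis test. Safety output is mostly listings, in which AEs and SAEs carry TEAE and relatedness flags. Doses are listed and onset dates are collected, so a late event can be identified. The overview table and the serious-TEAE part of the primary endpoint are what is exposed.

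**The SAP summarises subjects, not events. This stands.** SAP 6.1 gives numbers and percentages of subjects. A late related SAE adds nothing to a category in which that subject already counts, so the event-based illustrations tend to overstate the effect on the table.

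**Late reports are passive. This stands.** Neither Schedule of Events has a visit after End of Study. The share rises only if late related SAEs occur, are discovered and are entered.

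**Late SAEs may not reach the eCRF. This stands in part.** Protocol 10.9.5 says they are to be reported, and general AE recording closes at the End-of-study visit. However, 10.8.2 sends SAEs to the AE eCRF without a time limit, and the SAP provides for reconciliation, so entry is the more natural reading.

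**The timeframe mentioned in the late-SAE sentence could mean 28 days. This does not stand.** That reading would contradict the open-ended wording of the same sentence. The 24-hour reporting deadline in 10.9.4 fits better.

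**A stronger reading to avoid.** A reader might count only the days after last dose and infer a related share of 61% to 87% instead of 50% (43.5/28 = 1.55 to 180/28 = 6.43 related per unrelated event). The overview table does not work that way: it counts from the start of study drug, and on-treatment events are collected equally whatever their cause. Nor do the documents show that off-drug rates stay undiminished, or that the share of high-grade events must rise.

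**Conclusion.** The point holds. The SAP's definition, read with the protocol's collection rules, gives unequal capture by relatedness after about 28 days off drug. Compared with a common window, the related share of serious TEAEs can only be raised.

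The size cannot be known from the documents and is probably modest: about 51 to 58% instead of 50% under Illustration A, and 26 to 59% instead of 25% across Illustration B, with 32.5% in the middle case. It is zero if no late related SAE is reported, and smaller where the subject already counts. All of this rests on assumed constant rates and assumed durations on and off drug, and on late SAEs being entered in the AE eCRF.

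The documents do not support calling the distortion certain or large, and nothing here argues for reporting fewer late SAEs. Severity is minor to moderate.

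**What to change.** In SAP 6.6.1.1, state one fixed-day end to the TEAE window, counted from the last dose in the rollover study, applied by onset date and identical for related and unrelated events. Match it to the collection window: 28 days in Protocol 10.9.5, reconciled with the 28 ± 7-day visit in 10.8.2 and with the new-therapy limit in 10.9.5. A fixed day is better than the visit date, which can fall anywhere from day 21 to day 35 and is missing when a subject refuses the visit (Protocol 8 allows for refusal).

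Use only in-window events for the TEAE counts and the relationship split. Show later related SAEs in a separate row of the overview table and in a separate listing with days since last dose.

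The cost is a sentence or two in the SAP, one table row and one listing. The downside is that late related SAEs leave the headline TEAE count, though they stay fully reported. Safety reporting duties do not change.

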### 6.6.1.2 SUMMARY OF ADVERSE EVENTS

Adverse events (AEs) will be listed. Listings will be created by categories for AEs as outlined below:

- All adverse events (AEs) with flags for treatment emergent adverse events (TEAEs) and flags of relatedness to study drug(s)
- SAEs with flags for treatment emergent adverse events (TEAEs) and flags of relatedness to study drug(s)
- Immune related adverse events (irAEs)
- Infusion related reactions (IRRs)
- TEAEs leading to death
- TEAEs leading to study drug interruption, reduction, hold or permanent study drug discontinuation

## Statistical Analysis Plan Version draft

## Protocol JTX-2011-R01

A general overview summary table will also be provided include frequencies by category of AE (as listed above) and will also include TEAE by severity grade and relationship to study drugs.

#### 6.6.2 LABORATORY DATA

Laboratory data will be listed separately for hematology, chemistry, coagulation and urinalysis panels with lab results, normal ranges, CTCAE grade (as applicable).

#### 6.6.3 VITAL SIGNS AND ECG

Individual data listings will be provided for vital sign parameters: systolic and diastolic blood pressure (mmHg), respiratory rate (breaths per minute), body temperature (C°), weight (kg) and pulse rate (beats per minute).

**TABLE 1 NORMAL RANGE OF VITAL SIGNS**

Parameter	Units	Normal Range
Systolic Blood Pressure	mmHg	90 - 120
Diastolic Blood Pressure	mmHg	60 - 80
Pulse Rate	Beats per minute	60-100
Respiratory Rate	Breaths per minute	12 – 20
Temperature	°C	36.1 – 37.2

#### 6.6.4 ELECTROCARDIOGRAM (ECG)

Individual data listings will be provided, including observed and change from baseline values will be presented for ECG measures of PR interval, QRS duration, QT interval, QTc interval and overall interpretation.

#### 6.6.5 PHYSICAL EXAMS

Physical exam data will be presented in a data listing.

#### 6.6.6 EASTERN COOPERATIVE ONCOLOGY GROUP PERFORMANCE STATUS

The Eastern Cooperative Oncology Group (ECOG) performance status data will be presented in subject listings.

### 6.7 EXPLORATORY BIOMARKER ANALYSIS

Exploratory pharmacodynamic biomarkers collected in rollover studies will be listed when available.

There is no additional analysis planned for exploratory biomarkers for this study..

Statistical Analysis Plan Version draft

Protocol JTX-2011-R01

## 7. INTERIM ANALYSIS

Not applicable.

## 9. VERSION HISTORY

Version	Date	Summary of Changes	Reason for Change
1.0	01Dec2022	Initial document	Initial document
